3.1.3 Safety Monitoring Committee (SMC)

Safety and study conduct will be monitored throughout the study by the SMC, consisting of the study investigators and the sponsor responsible medical expert and biostatistician. The committee is tasked with monitoring the safety of participants in this study through regular or ad hoc meetings.

SMC activities related to evaluation of DLTs, recommending step-down dose levels for ZW25 and palbociclib, and recommending the doses for all the drugs in this combination to be used in Part 2 are described in [Section 3.1.2](#).

The SMC activities will be described in and governed by the SMC Guidelines.

3.1.4 Part 2 Anti-tumor Activity

The primary objective of Part 2 of the study is to evaluate the potential anti-tumor activity of the recommended dose level of the combination of ZW25 with palbociclib plus fulvestrant in subjects with a diagnosis of HER2-positive, HR-positive breast cancer that is locally advanced (unresectable) and/or metastatic.

Enrollment for Part 2 will begin once the recommended doses of ZW25 and the other drugs of the combination therapy have been confirmed in Part 1. The treatment and blood collection schedules, treatment cycle duration and imaging evaluation intervals are the same as in Part 1.

Part 2 of the study will evaluate the preliminary anti-tumor activity. All subjects will be assessed for safety and anti-tumor response. The mITT set includes all subjects who receive any amount of ZW25 with palbociclib and/or fulvestrant who had at least one identifiable (target and/or non-target) lesion at baseline and at least one post-baseline disease assessment or discontinued all study treatment and are no longer being followed for efficacy. The primary efficacy endpoint will be PFS6 (defined as the % of mITT subjects with PFS of ≥ 24 weeks); secondary efficacy endpoints include ORR, DOR, DCR, PFS, and OS. Approximately 50 subjects are expected to be enrolled in Part 2. Assuming the observed PFS6 rate is between 40% and 70%, the corresponding 95% binomial exact confidence intervals (CI) are summarized in [Table 4](#) below.

Table 4: PFS6 Rate and Corresponding 95% Confidence Intervals

PFS6 Rate	Binomial exact 95% CI (N=50)
40%	(26%, 55%)
50%	(36%, 64%)
60%	(45%, 74%)
70%	(55%, 82%)

Therefore, a total of up to approximately 86 subjects may be enrolled across the entire study.

If possible, an additional optional tumor biopsy may be obtained at the time of disease progression from an accessible site to allow for assessment of changes in HER2 expression as well as the presence of other exploratory biomarkers. Biomarkers of response may be evaluated.

3.1.5 Stopping Criteria

If the SMC recommends that the dose of ZW25 needs to be dropped below 15 mg/kg Q2W; the palbociclib dose needs to be reduced below 75 mg; and/or the fulvestrant dose needs to be reduced, then the study may be terminated.

The Sponsor reserves the right to terminate the study at any time for any reason.

For individual subjects, information on study treatment and study discontinuation is provided in [Section 4.4](#). Also, individual subjects may have to discontinue study treatment in case the dose modifications for ZW25 and palbociclib are not sufficient for managing toxicities ([Section 5.2.3](#) and [Section 5.3.3](#)).

3.2 Discussion and Rationale for Study Design

Although ZW25 has been evaluated as a single agent in a Phase 1 study and a single agent RD (20 mg/kg Q2W) has been confirmed, its tolerability when combined with palbociclib and fulvestrant in advanced or metastatic breast cancer has not been evaluated previously.

Part 1 of the study will first evaluate the safety and tolerability of ZW25 in combination with palbociclib plus fulvestrant and will confirm the RDs of all the drugs in this combination. Then, Part 2 of the study will evaluate the anti-tumor activity of ZW25 in combination with palbociclib plus fulvestrant (all drugs given at the RDs identified in Part 1) in subjects with HER2-positive, HR-positive breast cancer.

In summary, this study will evaluate the safety and preliminary anti-tumor activity of ZW25 combined with palbociclib plus fulvestrant in the treatment of subjects with advanced HER2-positive, HR-positive breast cancer that has progressed on or been refractory to prior treatment with trastuzumab, pertuzumab, and T-DM1. Premenopausal women and perimenopausal women will also be treated with an LHRH analogue (also known as gonadotropin-releasing hormone analogue) per institutional guidelines.

3.2.1 Method of Assigning Subjects to Treatment Groups

This is an open-label, non-randomized study. Subjects will be assigned to each cohort sequentially.

3.2.2 Rationale for Selection of Doses

To confirm the RD of ZW25 when combined with palbociclib and fulvestrant in subjects with breast cancer, Part 1 of the study is designed to address the question of whether the single-agent RD of ZW25 is tolerable when combined with palbociclib and fulvestrant. The initial doses to be explored will be a ZW25 monotherapy RD (20 mg/kg Q2W) from the Phase 1 study ZWI-ZW25-101 in combination with palbociclib per recommended dose (125 mg PO QD for the first 21 days of each 28-day cycle) in the package insert ([IBRANCE[®]](#)) and fulvestrant per recommended dose (500 mg IM Q2W for the first 3 doses, then Q4W thereafter) in the package insert ([FASLODEX[®]](#)). A step-down dose level of ZW25 (e.g., 15 mg/kg or other dose not lower

than 15 mg/kg Q2W) and/or palbociclib (e.g., 100 mg PO and/or 75 mg PO QD) may be allowed if recommended by the SMC. No step-down dose levels for fulvestrant are allowed; however, individual subjects with moderate hepatic impairment may receive a reduced dose per prescribing information. On Days 1 and 15 of each cycle, ZW25 will be administered first followed by palbociclib and fulvestrant. Premenopausal women and perimenopausal women will also be treated with a LHRH analogue (also known as gonadotropin-releasing hormone analogue) per institutional guidelines.

3.2.3 Blinding and Randomization

This is an open-label, non-randomized study.

4 STUDY POPULATION

Subjects must meet all of the enrollment criteria to be eligible for this study. All eligibility criteria are applicable to both parts of the study unless otherwise specified. Eligibility criteria may not be waived by the investigator and are subject to review in the event of a Good Clinical Practice (GCP) audit and/or health regulatory authority inspection.

4.1 Inclusion Criteria

Subjects must meet all of the following inclusion criteria.

1. Pathologically-confirmed diagnosis of breast cancer with evidence of locally advanced (unresectable) and/or metastatic disease. All subjects in both Parts 1 and 2 must have HER2-positive and HR-positive disease as follows:
 - HER2-positive based on the HER2 Testing in Breast Cancer: ASCO/CAP Clinical Practice Guidelines ([Wolff 2018](#)).
 - HR-positive defined as ER-positive and/or PgR-positive disease based on the ASCO/CAP Guideline Recommendations for Immunohistochemical Testing of Estrogen and Progesterone Receptors in Breast Cancer ([Hammond 2010](#)).
2. Able to provide a new formalin-fixed, paraffin-embedded (FFPE) tumor sample (preferred) or archived tumor tissue (most recent sample available) for retrospective central review of HER2 status.

Local assessments performed on a new tumor sample or archived tumor tissue in a Clinical Laboratory Improvements Amendments (CLIA)-certified lab using a combination of IHC and ISH/FISH methods may be used to determine HER2 and HR status for study eligibility. IHC must be used to determine HR status. Unless otherwise approved by the sponsor medical monitor, specimens should be provided for centralized retrospective review of HER2 status.

3. Received prior treatment with trastuzumab, pertuzumab, AND ado-trastuzumab emtansine (T-DM1); disease progression during or after the most recent prior therapy. Subjects in any part of the study who did not receive pertuzumab or T-DM1 because of lack of access (e.g., due to insurance coverage or because they were treated prior to regulatory agency approval of the agent in a relevant indication) or due to medical ineligibility for treatment with T-DM1 (e.g., history of severe infusion reactions to trastuzumab, \geq Grade 2 peripheral neuropathy, or

platelet count $< 100 \times 10^9/L$) may be eligible for the study after discussion with and approval from the sponsor medical monitor. Prior treatment with endocrine therapy in the neoadjuvant, adjuvant, and/or metastatic setting is permitted.

4. Sites of disease assessable per Response Evaluation Criteria in Solid Tumors (RECIST) version 1.1 (both measurable and non-measurable disease allowed)
5. Male and female subjects aged 18 years or older
6. An Eastern Cooperative Oncology Group (ECOG) Performance Status score of 0 or 1
7. Life expectancy of at least 3 months in the opinion of the investigator
8. The following baseline laboratory data:
 - a. Absolute neutrophil count (ANC) $\geq 1.5 \times 10^9/L$
 - b. Platelet count $\geq 75 \times 10^9/L$
 - c. Hemoglobin ≥ 9 g/dL
 - d. Prothrombin time (PT) and/or International Normalized Ratio (INR) and partial thromboplastin time (PTT)/ aPTT (activated partial thromboplastin time) $\leq 1.5 \times$ ULN, unless on medication known to alter the INR or PTT
 - e. Total bilirubin $\leq 1.5 \times$ ULN per institutional values (subjects with known Gilbert's Syndrome may enroll with $\leq 2.5 \times$ ULN provided the direct bilirubin is ≤ 1.5 mg/dL)
 - f. ALT $\leq 3.0 \times$ ULN per institutional values (if liver metastases are present, $\leq 5.0 \times$ ULN)
 - g. AST $\leq 3.0 \times$ ULN per institutional values (if liver metastases are present, $\leq 5.0 \times$ ULN)
 - h. Serum creatinine $\leq 1.5 \times$ ULN or calculated glomerular filtration rate ≥ 50 mL/min
9. Adequate cardiac left ventricular function, as defined by LVEF \geq institutional standard of normal
10. All toxicity related to prior cancer therapies must have resolved to \leq Grade 1, with the exception of alopecia or \leq Grade 2 neuropathy
11. If female and of child-bearing potential, must have a negative pregnancy test ≤ 3 days prior to the first dose of ZW25
12. For female subjects who are not surgically sterile or post-menopausal and for male subjects with a partner of child-bearing potential, willingness to use 2 methods of birth control with a failure rate of less than 1% per year during the study and for 12 months after the last dose of study drug (ZW25, palbociclib, and/or fulvestrant). These include, but are not limited to, established use of oral, implanted, or injected hormonal contraceptives; placement of intra-uterine device or intra-uterine system; or use of barrier methods, such as condom or diaphragm together with a spermicidal product.
13. Female subjects must agree not to breastfeed or donate ova starting at screening and throughout the study period, and for at least 12 months after the last dose of study drug (ZW25, palbociclib, and/or fulvestrant)

14. Male subjects must not donate sperm starting at screening and throughout the study period, and for at least 12 months after the last dose of study drug (ZW25, palbociclib, and/or fulvestrant)
15. Signed informed consent prior to any study procedures not considered standard of care

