1.6 Fulvestrant

Fulvestrant is an ER antagonist that binds to the ER in a competitive manner with affinity comparable to that of estradiol and downregulates the ER protein in human breast cancer cells. Fulvestrant is approved for the treatment of HR-positive, HER2-negative advanced or metastatic breast cancer in combination with palbociclib in patients with disease progression after endocrine therapy. The recommended dose of fulvestrant is 500 mg to be administered IM into the buttocks (gluteal area) slowly (1 to 2 minutes per injection) as two 5-mL injections, one in each buttock, on Days 1, 15, and 29 and once monthly thereafter ([FASLODEX[®]](#)).

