4.2 Exclusion Criteria

Subjects will be excluded from the study if 1 or more of the following criteria are applicable:

1. Prior treatment with trastuzumab, pertuzumab, lapatinib, T-DM1, or other anti-HER2-targeted therapy ≤ 3 weeks before the first dose of ZW25
2. Prior treatment with chemotherapy, other anti-cancer therapy not otherwise specified, or hormonal cancer therapy ≤ 3 weeks before the first dose of ZW25
3. Prior treatment with experimental biologic and non-biologic therapies ≤ 4 weeks before the first dose of ZW25
4. Prior treatment with radiation therapy other than for central nervous system (CNS) disease ≤ 3 weeks before the first dose of ZW25
5. Treatment with anthracyclines within 90 days before first dose of ZW25 and/or total lifetime load exceeding 360 mg/m^2 Adriamycin[®] or equivalent
6. Use of any medications or substances that are strong inhibitors or inducers of CYP3A isoenzymes within 7 days of first dose of any study drug
7. History of life-threatening hypersensitivity to monoclonal antibodies, recombinant proteins, or excipients in the drug formulation
8. Prior treatment with palbociclib or any other CDK4/6 inhibitors, including experimental agents
9. Use of corticosteroids administered at doses equivalent to > 15 mg per day of prednisone within 2 weeks of first ZW25 dosing unless otherwise approved by the sponsor medical monitor. Topical, ocular, intra-articular, intranasal, and/or inhalational corticosteroids are permitted.
10. History of myocardial infarction or unstable angina within 6 months prior to enrollment, troponin levels consistent with myocardial infarction, or clinically significant cardiac disease, such as ventricular arrhythmia requiring therapy, uncontrolled hypertension, or any history of symptomatic congestive heart failure (CHF)
11. QTc Fridericia (QTcF) > 470 ms
12. Grade 2 or greater pneumonitis and/or interstitial lung disease, including pulmonary fibrosis, or other clinically significant infiltrative pulmonary disease not related to lung metastases
13. Active hepatitis B or hepatitis C infection

14. Acute or chronic uncontrolled renal disease, pancreatitis, or severe liver disease (Child-Pugh Class C)
15. Known infection with Human Immunodeficiency Virus (HIV)-1 or HIV-2 (Exception: Subjects with well-controlled HIV [e.g., cluster of differentiation 4 (CD4)-positive T cell count $>350/\text{mm}^3$ and undetectable viral load] are eligible.)
16. Major surgery ≤ 3 weeks prior to the first dose of ZW25

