17. Prior or concurrent malignancy whose natural history or treatment has the potential to interfere with the safety or efficacy assessment of the investigational regimen
18. Any other medical, social, or psychosocial factors that, in the opinion of the investigator, could impact safety or compliance with study procedures
19. Females who are breastfeeding or pregnant, and females and males planning a pregnancy
20. Brain metastases: Untreated CNS metastases, symptomatic CNS metastases, or radiation treatment for CNS metastases within 4 weeks of start of study treatment. Stable, treated brain metastases are allowed (defined as subjects who are off steroids and anticonvulsants and are neurologically stable for at least 1 month at the time of screening).
21. Poorly-controlled seizures
22. History of or ongoing leptomeningeal disease (LMD). If LMD has been reported radiographically on baseline MRI, but is not suspected clinically by the investigator, the subject must be free of neurological symptoms of LMD.
23. Grade 3 or greater peripheral neuropathy

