4.3 Childbearing Potential

A person of childbearing potential is anyone born female who has experienced menarche and who has not undergone surgical sterilization (e.g., hysterectomy, bilateral salpingectomy, bilateral oophorectomy) or has not completed menopause. Menopause is defined clinically as 12 months of amenorrhea in a person over age 45 in the absence of other biological, physiological, or pharmacological causes.

A person who can father children is anyone born male who has testes and who has not undergone surgical sterilization (e.g., vasectomy followed by a clinical test proving that the procedure was effective).

According to the inclusion and exclusion criteria, pregnant or breast-feeding subjects cannot be included in the study, and adequate contraceptive measures should be taken to prevent female subjects of childbearing potential or female partners of male subjects (either of childbearing potential) from getting pregnant during study participation and for at least 12 months after the last dose of study drug (ZW25, palbociclib, and/or fulvestrant). Subjects will be instructed that known or suspected pregnancy occurring during the study should be confirmed and reported to the investigator. If a female subject is pregnant, the investigator will immediately discontinue the

subject from the study. Upon discontinuation, only those procedures that would not expose the subject to undue risk will be performed.

The investigator should also be notified of pregnancy occurring during the study or within 12 months following last study treatment administration but confirmed after completion of the study.

In the event that a female subject or female partner of a male subject is found to be pregnant after inclusion in the study, the pregnancy will be followed to term with subject/partner consent, and the status of mother and child will be reported to the sponsor after delivery and the status of the baby will be followed for a minimum of 6 months after a live birth.

Details of the pregnancy will be recorded on the withdrawal page of the case report form (CRF), and a Pregnancy Report Form will be completed.

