6.3 Treatment Period

Note: Throughout the treatment period, LHRH analogue will be administered to/taken by premenopausal women and perimenopausal women per institutional guidelines.

AEs and concomitant medications will be monitored and recorded throughout the treatment period.

6.3.1 Cycle 1

6.3.1.1 Cycle 1 Day 1

Prior to dosing:

- Confirm subject eligibility per inclusion/exclusion criteria
- Physical examination, including weight
- ECOG PS
- Vital signs
- Hematology, serum chemistry (plasma chemistry allowed if serum chemistry not available), and coagulation
- Pregnancy test (only for women of childbearing potential)
- Single 12-lead ECG
- ADA assessment sample
- Circulating tumor DNA (ctDNA) assessment sample
- HER2 ECD assessment sample

- PK assessment sample

Administer study treatment:

- ZW25 administration (Section 5.2.2)
- Palbociclib administration (Section 5.3.2)
- Fulvestrant administration (Section 5.3.2)

Postdose activities:

- Vital signs (within 30 minutes of the end of the infusion)
- Single 12-lead ECG (at 1 hour [± 15 minutes] after the end of ZW25 infusion)
- PK assessment sample(s)
- Dispense palbociclib and drug diary card along with instructions for taking it on an out-patient basis and recording date/time of doses on Days 2 through 21, except for Day 15 when the subject should arrive at the clinic before taking palbociclib

Note: Physical examination, ECOG performance status, and samples for hematology, serum chemistry, coagulation, and pregnancy (if applicable) tests may be done within 3 days prior to administration of study treatment and do not need to be repeated if done within the prior 3 days.

6.3.1.2 Cycle 1 Day 2

Subjects will take palbociclib QD (with food) on an out-patient basis.

Subjects on the extensive PK sampling schedule will report to the clinic to have a blood sample drawn.

Subjects on the sparse PK sampling schedule will not have a clinic visit.

6.3.1.3 Cycle 1 Days 3 and 4

No clinic visits.

Subjects will take palbociclib QD (with food) on an out-patient basis.

6.3.1.4 Cycle 1 Day 5

Subjects will take palbociclib QD (with food) on an out-patient basis.

Subjects on the extensive PK sampling schedule will report to the clinic to have a blood sample drawn.

Subjects on the sparse PK sampling schedule will not have a clinic visit.

6.3.1.5 Cycle 1 Days 6 through 14

No clinic visits.

Subjects will take palbociclib QD (with food) on an out-patient basis.

6.3.1.6 Cycle 1 Day 15

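### Criterion 12 accepts systemic hormonal contraceptives for female subjects who have HR-positive cancer and receive fulvestrant; elsewhere only norethindrone acetate is restricted

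*Combined protocol and SAP*

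**What the plan says.** Criterion 12 applies to two groups: female subjects who are neither surgically sterile nor past menopause, and male subjects whose partner could become pregnant. Throughout participation, and for a further 12 months once dosing has ended, both must show "willingness to use 2 methods of birth control with a failure rate of less than 1% per year". One list then serves both groups: "These include, but are not limited to, established use of oral, implanted, or injected hormonal contraceptives". Intra-uterine devices or systems and barrier methods with spermicide follow. Nothing in the list is reserved for partners. The synopsis repeats the criterion.

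On disease and treatment:
- Criterion 1: "All subjects in both Parts 1 and 2 must have HER2-positive and HR-positive disease as follows".
- Section 1.6: "Fulvestrant is an ER antagonist that binds to the ER in a competitive manner with affinity comparable to that of estradiol". Section 5.1 assigns fulvestrant to all subjects.
- Section 6.3, for the whole treatment period: "LHRH analogue will be administered to/taken by premenopausal women and perimenopausal women per institutional guidelines".

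On sex hormones as concomitant medication, the protocol has one statement: norethindrone acetate is contraindicated for these patients. It appears in the synopsis (under the LHRH analogue), in Section 5.2.7.1 and in Section 5.3.6.

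**The concern.** The women to whom criterion 12 applies are, in plain meaning, the pre- and perimenopausal women for whom the protocol adds an LHRH analogue to estrogen receptor antagonism. The criterion tells a site that a systemic estrogen or progestin product is acceptable contraception for them. For an affected woman, what is at stake is avoidable hormone exposure while she is treated for HR-positive advanced cancer with drugs meant to block estrogen signalling. The sponsor saw that at least one progestin is unsuitable here, but did not carry that into the two places where a site would settle the matter: the contraception criterion and the list of prohibited therapies.

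**Working it through.** This is a reading of the text. The plan states no figure on this point, so there is none to reproduce.

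**Step 1. Does any section limit the type of hormone in a female subject's contraception?**

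| Place | What it settles | Limits estrogens or progestins? |
|---|---|---|
| Criterion 12, synopsis and 4.1 | Acceptable methods | No; names systemic hormonal methods |
| 4.2, exclusion 2 | "Prior treatment with chemotherapy, other anti-cancer therapy not otherwise specified, or hormonal cancer therapy" in the 3 weeks before the first ZW25 dose | No; contraceptives are not cancer therapy |
| 4.3 | Asks for adequate contraception | No |
| 5.3.4.1 and 5.3.4.2 | Fetal risk of palbociclib and of fulvestrant; asks for effective contraception | No |
| 5.2.7 | Medication at entry is continued as needed unless prohibited for entry | No |
| 5.2.7.2 | Anything not listed as excluded or prohibited is allowed | No |
| 5.2.7.3 | Cancer surgery, radiotherapy, investigational and anti-neoplastic therapy, strong CYP3A4 inhibitors and inducers | No |
| Synopsis, 5.2.7.1 and 5.3.6 notes | Norethindrone acetate contraindicated | One compound only |

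Contraception comes up in 5 places (criterion 12 twice, 4.3, 5.3.4.1, 5.3.4.2), and 0 of the 5 limit the hormone type. The norethindrone note appears 3 times. It is repeated in neither criterion 12 nor 5.2.7.3.

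**Step 2. Follow one subject through the rules.** Take a premenopausal woman already on an oral contraceptive that does not contain norethindrone acetate, who also uses a second method. Criterion 12 counts the oral product toward her two methods. Exclusion 2 does not reach it. Section 5.2.7 says to continue it. Sections 5.2.7.2 and 5.2.7.3 together allow it. She then receives fulvestrant and an LHRH analogue alongside it, and no rule has been broken.

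**Step 3. Does such a product oppose the regimen?** For estrogens, Section 1.6 supports the inference directly: fulvestrant competes at the receptor with affinity comparable to estradiol. The LHRH requirement in 6.3 points the same way. For progestins, the support is thinner: HR-positive includes PgR-positive disease, and the norethindrone notes name one progestin. No section states that hormonal contraception impairs the treatment.

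**Step 4. How many women?** The plan does not give the number of pre- and perimenopausal subjects, nor the number using a systemic hormonal method. The range runs from 0 to the unstated number of pre- and perimenopausal women among up to approximately 86 subjects.

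**Step 5. What does removing these methods do to the below-1% standard?** The protocol gives no failure rate for any method, and does not say whether the standard applies to each method or to the two together. As an assumption, let a barrier method fail at 5% to 30% per year, independently of the other method.
- Standard applied to each method: 5% to 30% is above 1% throughout.
- Standard applied to the pair, two barrier methods: 0.05 × 0.05 = 0.25% up to 0.30 × 0.30 = 9%. This is below 1% only if each method is below √0.01 = 10%.

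So a woman limited to barrier methods may not meet the standard. That is the real cost of the change.

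**The case against.** The strongest reply is that the harm is inferred and the exposure small. The list concerns established use, so it does not prompt anyone to start a hormonal method, and it names other methods too. These are women with advanced, pretreated cancer under oncology care. Exclusion 18 lets an investigator exclude for "Any other medical, social, or psychosocial factors that, in the opinion of the investigator, could impact safety or compliance with study procedures". Section 5.1 gives local prescribing information for palbociclib and fulvestrant priority where it conflicts with the protocol. The norethindrone note sits in both concomitant-therapy sections.

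Most of this stands, and it keeps the point small. It does not remove it. Established use is exactly the case in which Section 5.2.7 says to continue. Exclusion 18 and Section 5.1 are general safeguards, and neither is a rule on contraceptive type. An eligibility criterion should not endorse a method that then has to be overridden by judgement.

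The reply is also right that some remedies would go too far. The documents do not support banning hormone-releasing intra-uterine systems: the mechanism text does not address them. Nor is there reason to rewrite the failure-rate standard. Applying it to the pair would be a separate change that could relax it, and palbociclib and fulvestrant can both cause fetal harm. The argument from the regimen covers study treatment, not the 12 months of contraception required afterwards.

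**Conclusion.** The point holds as a cheap improvement to patient protection. Criterion 12 accepts systemic hormonal contraceptives for female subjects with HR-positive cancer on fulvestrant (plus an LHRH analogue if pre- or perimenopausal), and nothing but the norethindrone notes limits them. The textual finding is firm. The consequence rests on a clinical inference from Sections 1.6 and 6.3 and the norethindrone notes, better supported for estrogens than for progestins. The number affected is unknown and probably small.

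Three stronger readings are tempting, and the documents support none of them:
- That the protocol contradicts itself. A site can obey criterion 12 and the norethindrone notes together; the notes sit with the LHRH text and do not mention contraception.
- That PFS6 would be biased. The documents give no basis for estimating an effect, and the sample size and confidence interval calculations are untouched.
- That women are steered to hormonal methods. The list is open-ended and names intra-uterine and barrier methods.

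**What to change.** **Criterion 12 (Section 4.1 and synopsis).** State that oral, implanted or injected hormonal contraceptives are acceptable only for female partners of male subjects. Female subjects use the intra-uterine or barrier methods already listed, or other non-hormonal methods. One example is a male partner with a confirmed vasectomy, for which Section 4.3 already has the wording: "vasectomy followed by a clinical test proving that the procedure was effective". Keep the two-method and below-1% wording unchanged. Make clear that the restriction is aimed at the period of study treatment.

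**Section 5.2.7.3.** Prohibit systemic estrogen- or progestin-containing products, including norethindrone acetate, for subjects during study treatment. Any such product is stopped during the 28-day screening period, before Cycle 1 Day 1: no further doses, and an implant removed. The documents give no basis for a washout length, so an injected product may still be active at the first dose.

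**Hormone-releasing intra-uterine systems.** Do not ban them; refer each case to the medical monitor.

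**Cost.** A wording change in two copies of criterion 12 and an added entry in 5.2.7.3. Sample size, visits and analyses do not change. The downside is fewer options for female subjects: a woman who cannot use an intra-uterine device may have difficulty meeting the below-1% standard and so may not be eligible. Given the fetal risk stated in Section 5.3.4, the standard should not be loosened to accommodate her.
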